a) Negative and cognitive symptoms. We hypothesize that negative symptoms and cognitive impairment (measured by BPRS subscales) will correlate negatively with weight loss. Motivation (measured by the URICA) and illness insight (measured by the SAIQ) will be positively correlated with weight loss.

b) Treatment adherence. SMI veterans involved in the Lifestyle Balance Program will have better adherence to psychiatric treatment than the "usual care" group as measured by a treatment adherence questionnaire, percent of antipsychotic medication refills and percent of appointments attended.

c) Ongoing informed consent. Consent is to be an ongoing process and we hypothesize that SMI veterans involved with the program will continue to give informed consent to participate. This will be demonstrated by subjects' performance on the informed consent quiz at 0, 6, and 12 months of participation.

II. Background and Significance

A. Overview of Obesity in the SMI Population: [Definitions: "Obesity" is defined as a body mass index of ≥ 30 . "Overweight" is defined as a body mass index of ≥ 25 . Body mass index (BMI) is a ratio of person's weight in kg divided by their height in meters squared. Severe mental illness (SMI) includes schizophrenia, bipolar disorder, severe recurrent depression, obsessive-compulsive disorder, and panic disorder] Obesity is a severe public health problem in the United States that shortens our lives due to its association with a number of diseases, including diabetes, cardiovascular illness, and several forms of cancer

(4). Obesity is “outweighing” smoking as the number one modifiable risk factor for cardiovascular disease and death in this country. Obesity is an even greater problem for patients with SMI. The SMI have a higher all-cause mortality rate than the normal population with suicide and cardiovascular disease accounting for the lion’s share of the early deaths (5-7). Given a smoking prevalence sometimes exceeding 75% it is not surprising that cardiovascular disease remains the leading cause of premature deaths.

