Prior to statistical analyses, the data will be inspected to determine the advisability of scale transformation to normalize distributions or reduce variance heterogeneity (e.g., logarithmic or power transformations) and to identify missing data, outliers, or other unusual features that might bias results. Where multiple measures may overlap or be redundant, preliminary analyses will explore whether it is possible to reduce these using techniques from scale development such as factor analyses. Preliminary analyses are also performed to compare treatment groups on descriptive and clinical characteristics at baseline to ensure randomization has succeeded. If there are significant differences between the treatment groups at baseline we will create propensity scores and include them in all further analyses as covariates to compensate for potential bias. We will also test if there are significant site effects, and if necessary we will include a site variable in the mixed linear model analysis, and model time as nested in subjects and subjects nested in sites.

To address concerns about excessive Type I error rates, the principal analyses are designed to answer clearly stated major research hypotheses, and are based on well-specified dependent variables. The samples are large enough to expect that confidence limits may be reasonably narrow, and findings may be robust enough to permit conservative adjustments of p-values for multiple testing. Bonferroni and other adjustments are necessarily somewhat arbitrary as Saville notes in his argument against their use (71). Additional analyses that are exploratory will be clearly identified as such. All tests will be two-tailed at $\alpha=0.05$.

2. Attrition: Dropout from treatment does not necessarily mean participants will refuse follow-up assessments, and we will attempt to obtain full follow-up data on all enrolled participants regardless of degree of participation and include all enrolled participants in analyses when any outcome data are available (intent to treat). Attrition can compromise randomization, so preliminary analyses will compare baseline characteristics

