It provides valid statistics even in cases where there are more potential predictors than observations, and allows us to include all demographic, psychosocial, psychiatric and medical data known at baseline as potential predictors. The results of this analysis will suggest which patients are most likely to profit from further interventions, and it will also characterize the most at risk patients.

c) Subjects will continue to give meaningful, informed consent to participate throughout the study. They will see no significant decrease in their score on the informed consent quiz given every 6 months.

Analysis plan: A general linear model (GLM): ANOVA will be performed to compare the informed quizzes score results at 0, 6, and 12 months during the subjects' participation in the study.

5. Power Analysis: All calculations are based assuming a conventional medium effect size ($f=.25$, Cohen 1988); and a two-tailed alpha set at 0.05. Tuomilehto et al. estimated the SD of weight loss at roughly 5 kg across several treatment conditions (lifestyle changes vs. control) (76). A medium effect would thus translate into a group difference of about 2.5 kg or about 5.5 pounds. With an enrollment of $N=120$ and an estimated attrition rate of 45% we expect that at least 66 subjects will provide complete the study and provide 4 data points. The power analyses below are based on a sample size of $N=66$, i.e. this is a very conservative estimate due to the fact that the mixed linear model allows us to include cases with missing values in the analyses and that while they don't provide as much information as complete cases they still provide some information and will increase power. For the between-group comparisons, $N=66$ yields power=.7199 for main differences between groups if we assume that the within subject correlation is $r=.50$. Power to test for the difference in outcome trajectories of time – our main outcome variable is 0.99, and even if the effect is as small as $f=0.15$ we will have sufficient power to distinguish between the trajectories of the two treatment groups (power=0.83) insuring that we will get significant, insuring that we Preliminary data analyses shows that these assumptions are quite conservative and that effect sizes seem to be slightly larger than projected, suggesting that the final power will exceed the estimates presented here.

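### Maintained understanding of consent is judged by the absence of a significant fall in quiz scores, so fewer or noisier quizzes make the favourable conclusion easier to reach

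*Combined protocol and SAP*

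**What the plan says.** The hypothesis appears twice in the combined protocol and SAP.

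- **Section I.D (Hypotheses), secondary hypothesis (c)** expects veterans in the program to go on giving informed consent, and adds: "This will be demonstrated by subjects' performance on the informed consent quiz at 0, 6, and 12 months of participation".
- **Section V.N, Statistical Plans, secondary hypothesis (c)** restates it as "Subjects will continue to give meaningful, informed consent to participate throughout the study", followed by the criterion: "They will see no significant decrease in their score on the informed consent quiz given every 6 months". The analysis is one sentence: "A general linear model (GLM): ANOVA will be performed to compare the informed quizzes score results at 0, 6, and 12 months".

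The general rule in Section V.N.1 is two-sided testing at 0.05. No margin, minimum score, interval criterion or power statement is attached to the quiz.

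Three other places bear on the point:

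- **Attrition (V.N.2)** aims to follow everyone enrolled and to analyse all who have any outcome data.
- **Repeated measures analyses (V.N.3)** describes a mixed model that tolerates missing visits and says that it serves all cross-sectional and linear hypotheses.
- **Power Analysis (V.N.5)** states the expected loss: "With an enrollment of $N=120$ and an estimated attrition rate of 45% we expect that at least 66 subjects" will complete.

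**The concern.** The hypothesis is that scores do not fall. The test named looks for a difference, and the stated criterion is met when none is found. A non-significant result can mean that scores held up, or that there were too few quizzes to tell, and this criterion cannot separate the two. In the usual superiority test, dropout and noise count against the investigator's hypothesis. Here they count in its favour.

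At stake is a published statement that patients with severe mental illness kept their understanding of a year-long study. The Informed Consent section of the plan itself notes the controversy over whether such patients can give meaningful consent, so that statement should rest on positive evidence.

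**Working it through.** **Inputs from the documents.** 120 enrolled and 45% attrition (Power Analysis); three quiz times (Statistical Plans); two-sided alpha 0.05 (V.N.1).

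**Assumptions.** The quiz SD, the correlation between quizzes and the size of any decline are not in the documents. Declines are therefore expressed in SD units, for 0.2, 0.3 and 0.5 SD. The within-subject correlation r = 0.50 is borrowed from the Power Analysis, where it serves a different comparison, and is varied from 0.3 to 0.7.

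**Step 1: reproduce the plan's own figures.** Completers: 120 × (1 − 0.45) = 66. Power for two groups, four time points and r = 0.5, from the noncentral F distribution:

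- Between groups, f = 0.25: λ = f²·N·m / [1 + (m − 1)r] = 0.0625 × 66 × 4 / 2.5 = 6.6 on 1 and 64 df. Power is 0.716 (plan: .7199).
- Trajectories, f = 0.25: λ = f²·N·m / (1 − r) = 0.0625 × 66 × 4 / 0.5 = 33 on 3 and 192 df. Power is 0.999 (plan: 0.99).
- Trajectories, f = 0.15: λ = 0.0225 × 66 × 4 / 0.5 = 11.88. Power is 0.828 (plan: 0.83).

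The method matches the plan's figures closely.

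**Step 2: apply it to the quiz.** For a linear decline of d SD by month 12 the three means are 0, −d/2 and −d. Their variance is f² = d²/6, so λ = 3N·f² / (1 − r) = d²·N / [2(1 − r)], on 2 and 2(N − 1) df. At r = 0.5 this is λ = d²·N.

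| True decline | N | λ | Chance of a non-significant result |
|---|---|---|---|
| 0.2 SD | 66 | 2.64 | 72% |
| 0.3 SD | 66 | 5.94 | 43% |
| 0.5 SD | 66 | 16.5 | 4% |
| 0.2 SD | 120 | 4.8 | 52% |
| 0.3 SD | 120 | 10.8 | 16% |
| 0.5 SD | 120 | 30 | 0.1% |

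At 0.3 SD with 66 completers the figure runs from 20% (r = 0.7, λ = 9.9) to 57% (r = 0.3, λ = 4.24). The planned loss of 54 patients alone moves it from 16% to 43%, towards the favourable conclusion.

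**Step 3: what a margin-based rule could deliver.** Take the change from baseline to month 12, with SD √[2(1 − r)] = 1 at r = 0.5, no true change, and a one-sided 0.025 limit. Power = Φ(margin × √66 − 1.96), with √66 = 8.124:

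- margin 0.2 SD: Φ(−0.335) = 37%
- margin 0.3 SD: Φ(0.477) = 68%
- margin 0.5 SD: Φ(2.102) = 98%

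**The case against.** The best defence has four parts.

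1. **The plan never says that a null F test will be reported as proof.** It says that scores will be compared, and performance on the quiz need not mean a p-value. This is literally true. But the criterion is worded in terms of significance, the hypothesis section says that the quiz will demonstrate continuing consent, and no other decision rule is offered.

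2. **Power is not low for every decline.** This stands. At the plan's own medium effect, f = 0.25, the linear decline is 0.25 × √6 = 0.61 SD, and it would be missed less than 1% of the time. At f = 0.15 (0.37 SD) it would be missed about 24% of the time. The documents do not say which decline would matter.

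3. **Missing data are already addressed.** This stands in part. A reader might infer a completers-only analysis, but the documents do not say so: the Attrition and Repeated measures sections point the other way. The analysis sentence names an ANOVA while the neighbouring hypothesis (b) names mixed models, so coverage of the quiz is ambiguous. A mixed model would recover data without changing the success criterion.

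4. **Patients are protected in other ways.** This stands. A reader might infer that they would be left in the study without understanding it. The Informed Consent section, however, re-checks each patient at least every six months, whatever the group mean shows.

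Two other strong readings also go too far. An analysis that ignored pairing would miss a 0.3 SD decline about 69% of the time with 66 per time point, but nothing in the plan proposes one, and V.N.3 stresses observing the same subjects over time. Discharge for worsening on the CGI (Minimizing Risks) might selectively remove patients whose understanding is falling, but the documents do not link CGI change to quiz scores.

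**Conclusion.** The point holds as a fault in the decision rule: absence of a significant fall is not evidence that understanding was maintained. That conclusion needs no numerical assumption.

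Its practical size does depend on assumptions. With 66 completers, a paired analysis and r = 0.5, the rule is weak for declines of 0.2 to 0.3 SD and reliable at 0.5 SD. These rates illustrate the problem; they do not predict this trial's result. They also assume a linear decline and dropout unrelated to the quiz.

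It is worth correcting because the change is cheap and prevents an unsupported claim about a sensitive matter. It concerns one secondary hypothesis and does not touch the weight or metabolic conclusions.

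**What to change.** Replace the criterion and the analysis sentence for secondary hypothesis (c) with the following.

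- **Estimate.** Mean change in quiz score from baseline at 6 and 12 months, with confidence intervals, from the mixed model of V.N.3 using all available quizzes.
- **Population.** State which arms are included. The hypothesis section refers to veterans in the program, the analysis section to subjects in general.
- **Rule.** Fix the largest acceptable decrease before analysis. Conclude that understanding was maintained only if the lower confidence limit lies above it. Otherwise report the estimate and interval as inconclusive.
- **Individuals.** The documents give no pass mark. If the sponsor sets a minimum score, also report the proportion meeting it at each time, since a mean cannot show that each patient still understands.

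The cost is a few lines of SAP text and one margin; the quizzes are already scheduled. The downside is that the claim becomes harder to reach. With no true change, 66 completers and r = 0.5, it would be reached about 37%, 68% and 98% of the time at margins of 0.2, 0.3 and 0.5 SD. These figures are for month 12 alone; requiring month 6 as well would lower them. The margin should be chosen for what loss of understanding is tolerable, not for what the sample can exclude.

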3. Repeated measures analyses: We propose to longitudinal (repeated measures) analyses to maximize the additional power we gain by observing the same subjects across 12 months.. Repeated measures analyses permit contrasts at each time point, and also describe and compare trajectories of change (trends), speed and durability of effects. We will also conduct separate cross-sectional to provide outcome data for ongoing safety review, interim progress reports, study oversight and conduct.

The primary design for longitudinal (repeated measures) analyses of continuous outcome scales will be a 2-group (treatment) mixed general linear model of timepoints nested within participants. This is very general linear model that permits flexibility in specifying the nature of the covariances among the dependent measures, allows time-dependent, within and between subject covariates, and permits incomplete (i.e., missing) data. Analyses of trends across the monthly assessments will be done using growth curve model within the mixed model analysis of covariance design with repeated measures described above. We propose to model a linear trend of time unless inspection clearly suggests nonlinearity. By fitting a slope over time (and intercept) for each participant who has baseline and at least one other measure, this method makes good use of all the data, and is robust even if some of the some measures are missing. The use of the mixed general linear model for all cross-sectional and linear hypotheses ensures that results will be comparable across different analyses and provide a framework to include group, person and time-specific covariates if it becomes necessary. The preliminary analyses have shown that this analysis strategy provides meaningful results even with partial data and suggests that we will exceed the originally projected power.**4. Stratification:** Randomization will be stratified by type of antipsychotic and presence of mood stabilizer medication (e.g., depakote, lithium) to assure balance on olanzapine and clozapine by randomizing within three strata – olanzapine, clozapine, and all other antipsychotics -- using three separate randomization lists. Because such stratification can adversely affect statistical power by creating artificially comparable (and heterogeneous) groups, two dummy variables coding olanzapine and clozapine at baseline will be included in all analyses as covariates.

4. Statistical Plans:

Primary Hypotheses:

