Analysis plan: We do not expect to see meaningful weight loss in the usual care group, and thus do not expect meaningful correlations based on these hypotheses. Accordingly, the primary tests of each of these hypotheses will be done by computing Pearson correlations between the specified variables within the treatment group. Supplementary analyses will be done within the context of the mixed effects designs described above, including these variables as possible treatment effect moderators. Separate analyses for hypotheses (i.) through (iv.) above will be done to examine possible interactions of each of these variables considered separately with treatment group. These analyses will test whether treatment may be more or less effective as a function of these variables (negative symptoms, motivation to change, cognitive cluster, insight). If so, we will stratify the groups according to these variables to simplify presentation of the results, e.g., treatment outcomes presented separately in groups with more versus less cognitive impairment).

b) SMI patients involved in the Lifestyle Balance Program will have better adherence to psychiatric treatment than the Usual Care group as measured by percent of psychotropic medication refills and percent of appointments attended.

Analysis plan: We will compute these dependent measures (percent of psychotropic medication refills and percent of appointments attended) to create summary scores within each of the three study follow-up epochs (baseline- 8 weeks, 8 weeks- 6 months, 6-12 months). These will be analyzed using general linear mixed effects models with repeated measures, including baseline stratification medication as a covariate. We will test group, time and interaction effects, and perform between-group contrasts for each time period.

To determine what patient characteristics, e.g. Medication group, diagnostic or symptom status is most conducive to positive outcome we will use classification analysis using the recursive partitioning algorithm to determine which patient characteristics at baseline are the best predictors for positive outcomes. Recursive partitioning is a computationally intense data mining technique that allows for the analysis of multiple predictors simultaneously while protecting against type I error inflation due to multiple testing and it provides non-parametric confidence intervals by using cross-validation (75).

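### The consent-quiz analysis names a GLM ANOVA with no patient term for scores repeated within patients; the plan's own mixed model should be named instead (minor)

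*Combined protocol and SAP*

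**What the plan says.** Secondary Hypothesis (c) is that patients keep giving meaningful consent. Section I.D.2(c) rests it on "performance on the informed consent quiz at 0, 6, and 12 months of participation", and the Schedule of Events places the quiz at the same three visits. Under 4. Statistical Plans (section V.N), success is worded as "They will see no significant decrease in their score on the informed consent quiz given every 6 months". The analysis sentence that follows is "A general linear model (GLM): ANOVA will be performed to compare the informed quizzes score results at 0, 6, and 12 months". It names no patient term, covariance structure or error term.

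Elsewhere the plan is explicit about repeated data. N.3 (Repeated measures analyses) sets the design for continuous outcomes as a "mixed general linear model of timepoints nested within participants". The analysis plan for the primary hypotheses nests timepoints in patients. For Secondary Hypothesis (b), immediately before (c), the plan says of the adherence measures: "These will be analyzed using general linear mixed effects models with repeated measures". N.3 also makes a general statement: "The use of the mixed general linear model for all cross-sectional and linear hypotheses ensures that results will be comparable across different analyses".

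**The concern.** Three quiz scores from one patient are correlated, and the named procedure says nothing about this. It can be run in two ways, and neither matches the model used for the neighbouring hypothesis.

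- **Ordinary ANOVA on three sets of scores.** Differences between patients go into the error term, the F statistic is too small, and confidence intervals for the change over time are too wide.
- **Classical repeated-measures ANOVA.** The pairing is respected, but normally only patients with all three quizzes are used. N.2 (Attrition) cites a comparison of methods that warns against relying on complete cases alone.

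The direction matters because a non-significant result counts as support. A test that rejects too rarely leans towards the conclusion the plan hopes for, on understanding of consent in a population whose ability to consent the protocol itself describes as disputed (section V.C).

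**Working it through.** **The plan's own figures first.** N.5 (Power Analysis) gives no power, SD or effect for the quiz. Its outcome figures use N = 66, two groups, four timepoints, within-subject r = 0.50 and alpha 0.05. They reproduce with noncentral F:

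- Group effect, f = 0.25: lambda = N·f²·m/(1 + (m − 1)r), df 1 and 64. Power 0.716 (stated 0.7199).
- Group by time: lambda = N·f²·m/(1 − r), df 3 and 192. Power 0.999 at f = 0.25 (stated 0.99) and 0.828 at f = 0.15 (stated 0.83).

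**Inputs for the quiz.**
- From N.5: 120 enrolled; 45% attrition, so 120 × 0.55 = 66 completers; f = 0.25.
- Assumed: 90 quizzes at month 6; r = 0.5, borrowed from N.5's outcome calculation, with a range shown; normal scores with equal SD and equal correlation; linear decline of d SD by month 12; dropout unrelated to score. Patients with one, two and three quizzes are then 120 − 90 = 30, 90 − 66 = 24, and 66.

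**Scale.** For means 0, −d/2, −d the variance of the means is d²/6, so f = d/√6. The plan's f = 0.25 is d = 0.25 × 2.449 = 0.61 SD.

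**Why the ordinary ANOVA is conservative.** With complete data and no change, the expected mean square for time is σ²(1 − r), while the one-way error mean square is about σ². At r = 0.5 the F ratio is about half what its reference distribution assumes. With 120/90/66 quizzes, simulation gives a true size of about 0.8% at nominal 5% (about 2% at r = 0.3; 0.3% or less at r = 0.7).

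**Repeated-measures ANOVA, 66 complete patients.** lambda = 3N·(d²/6)/(1 − r), df 2 and 130.
- d = 0.3: 198 × 0.015/0.5 = 5.94, power 0.57.
- d = 0.4: 198 × 0.02667/0.5 = 10.56, power 0.83.
- d = 0.61: 198 × 0.0625/0.5 = 24.75, power 0.996.

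**Mixed model, all quizzes.** Sum each patient's information matrix over the 30, 24 and 66 patients and take the 2-df Wald test of visit (denominator df 132). At r = 0.5 and d = 0.3, lambda = 7.04 and power is 0.65.

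| Decline by month 12 | r | Ordinary ANOVA | Complete-case RM ANOVA | Mixed model |
|---|---|---|---|---|
| 0.3 SD | 0.5 | 0.34 | 0.57 | 0.65 |
| 0.4 SD | 0.5 | 0.65 | 0.83 | 0.89 |
| 0.61 SD | 0.5 | 0.98 | 0.996 | 0.999 |
| 0.3 SD | 0.3 | 0.36 to 0.38 | 0.42 to 0.43 | 0.51 |
| 0.3 SD | 0.7 | 0.30 | 0.80 | 0.855 |
| 0.3 SD | 0.1 | 0.40 | 0.34 | 0.43 |

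Ordinary ANOVA figures are simulated; the 0.36 to 0.38 is the spread between simulation runs.

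**The case against.** The strongest reply is that the plan never says the scores are treated as independent. A repeated-measures ANOVA is itself a general linear model, and N.3's general sentence can be read as bringing the quiz under the mixed model, with the later wording as shorthand. This stands in part. A reader might infer that the plan ignores the pairing outright; the text does not support that, because the error term is simply unstated. But a general sentence does not clearly override a specific instruction naming a different procedure, especially when the hypothesis just before it names repeated measures. An analyst following the quiz sentence could run either test.

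A reader might also infer that the ordinary ANOVA misses real loss that the mixed model would detect. That is too strong. At 0.3 SD and r = 0.5 the mixed model still misses about 35%, and at the plan's medium effect the three tests barely differ. Correlation may also be low: patients who cannot consent are excluded and the material is taught interactively, so scores may be compressed. At r = 0.1 the mixed model gains only 3 points over the ordinary ANOVA.

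Finally, a reader might infer that participants lose protection. Section V.C has each patient's understanding re-checked at least every 6 months. That individual check is the safeguard, not this group comparison.

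**Conclusion.** The point holds as a mismatch between the named test and the paired data, and as a departure from the model the plan uses for its other repeated outcomes. Its size depends on the reading. Under the ordinary ANOVA, at 0.3 SD and r = 0.5, power falls by about 31 points (65 − 34). Under the repeated-measures ANOVA the loss is about 8 points at 0.3 SD (65 − 57) and 6 at 0.4 SD (89 − 83). Both results rest on the assumed r, the assumed 90 quizzes at month 6, linear decline and dropout unrelated to score.

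Severity is minor: the hypothesis is secondary and not about efficacy, and only small to moderate declines are affected. The plan also infers maintained understanding from non-significance without a margin for acceptable decline. That is a separate issue, and changing the model does not resolve it.

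**What to change.** In the analysis plan for Secondary Hypothesis (c), replace the GLM ANOVA with the plan's mixed general linear model: quiz score at 0, 6 and 12 months, visit as a categorical fixed effect, timepoints nested within patients, every available quiz included. Report the within-patient changes from 0 to 6 and from 0 to 12 months with 95% confidence intervals; any margin set later would be judged against these.

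The cost is one sentence in the SAP. No new data, patients or visits are needed, and the model is already in use for the other outcomes.

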Methods: This pilot research was approved by the IRB and oral informed consent was obtained from all participants. All inpatients on an acute inpatient schizophrenia treatment unit were invited to attend a 30-minute presentation given once per week by a medical student and a pre-doctoral psychology assistant under the supervision of the primary investigator. The interactive class material included the health benefits of maintaining one’s ideal body weight, making food choices according to the USDA Food Pyramid, proper portion sizes, healthy meal choices when eating outside the home, and the importance of beginning and adhering to an exercise program.

Results: **Subject Demographics:** Of the subjects, 93% were male and 7% were female. Most of the subjects were middle-aged, with 85% of the sample falling between the ages of 41 and 60 years of age. 24% of those sampled did not graduate high school, 20% had graduated or had a GED, 35% had at least some college education, and 20% had post-college training. Of the male patients sampled, 37% were overweight and another 37% obese, with only 26% of normal weight. Of the two female patients sampled, one was overweight and the other obese. **Eating Behaviors:** Most patients indicate that they eat the majority of their meals outside of their place of residence, with only 41% eating most of their meals at their own home. The remaining patients ate most meals at fast food restaurants (23%), at board and care facilities (21%), at the homes of family members (13%), or at other restaurants (3%). Only 23% of patients prepared one or more of their meals each day. 20% prepared their own meals 3 times per week, and 22% once a week or less. 33% never cook at all. **Knowledge Quiz:** 70 subjects chose to participate and completed the pretest, 50 patients completed both the pre- and post-presentation tests. The mean percentage of correct answers on the pre-test was 85.6%, which rose on the post-test to 89.3%. This difference of 3.7% is statistically significant ($t = 2.43$, $df = 49$, $p < 0.02$), and the mean percent of improvement ($\% \text{difference} / \text{pretest } \% \text{ correct}$) was 6.1%. Educational level of the patients was not correlated with the final percentage of correct answers ($r = 0.06$, $p = \text{NS}$), nor with improvement in test scores ($r = -0.28$, $p = \text{NS}$). In addition, 73% of the subjects expressed a desire to lose weight.

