a) SMI patients with antipsychotic associated obesity who participate in a behavioral intervention that includes classes on Lifestyle Balance will gain more knowledge (i.e., greater change scores on before/after survey test instrument) about general health issues (e.g., nutrition, importance of exercise.) than a control group receiving “usual psychiatric care”.

b) SMI patients with antipsychotic associated obesity who participate in a behavioral intervention program will achieve better cardiovascular (e.g., sustained weight loss, better glucose tolerance, improved lipid profiles, and improvement in other biological measures, e.g. insulin and c-reactive protein) and mental health (e.g., improvements in general measures of psychopathology, subjective quality of life, etc) outcomes than the control group. A larger proportion of patients who take the Lifestyle Balance classes will actually make lifestyle

changes (objectively measured by food and exercise diaries) than patients in the usual care group given ordinary counseling.

c) A larger proportion of patients who take the Lifestyle Balance classes will actually make lifestyle changes (objectively measured by food and exercise diaries and exit interviews) than patients in the usual care group given ordinary counseling. Analysis plan: For all hypotheses concerning the effects of the treatment program use analysis of repeated measures using the assessments at baseline, 8 weeks, 6 months, and 12 months. These analyses will provide information about maintenance of treatment effects. We will use a mixed general linear model with timepoints nested within patients. For hypothesis (c) we will adapt the mixed general linear model to dichotomous data by using a logistic link function to model the likelihood of life style changes. We will include all patients with at least one post-baseline data point in the analysis to maximize power. We will also consider the appropriateness of linear growth curve mixed effects models, i.e., fitting an intercept and linear slope for each treatment group as fixed effects, and separate intercepts and linear slopes for each patient as random effects. Analyses of linear trends over time with a single df effect are often more powerful tests of differences in trends than multiple df profile contrasts across the separate time points.

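### N.5 expresses f=.25 as 2.5 kg using an SD of weight change, which does not fit a group main effect on weight with baseline among the four responses

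*Combined protocol and SAP*

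**What the plan says.** V.N.5 bases every power figure on Cohen's conventional medium effect, f=.25, with a "two-tailed alpha set at 0.05". The only measure of variability it cites is that an outside study "estimated the SD of weight loss at roughly 5 kg across several treatment conditions". From this it concludes: "A medium effect would thus translate into a group difference of about 2.5 kg or about 5.5 pounds". The sample size follows in the words "With an enrollment of $N=120$ and an estimated attrition rate of 45" per cent, leaving 66 patients with four data points each. For the between-group comparison it then states "N=66$ yields power=.7199 for main differences between groups if we assume that the within subject correlation is $r=.50". For the group difference in trajectories, which it calls the main outcome, it gives 0.99, and 0.83 at f=0.15.

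The analysis plan in V.N.4 says it will "use analysis of repeated measures using the assessments at baseline, 8 weeks, 6 months, and 12 months". V.N.3 fits an intercept and a slope to each participant who has baseline and at least one later measure. The covariates it names for all analyses are indicators for olanzapine and clozapine at baseline; baseline weight is not named. V.G.2 has weight measured at every visit.

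**The concern.** A change from baseline is zero at baseline, so four informative data points that include baseline fit weight itself, not weight change. In a group main effect on weight, the error term contains the variation in weight between patients. An SD of weight change largely removes that variation. N.5 therefore sets a kilogram value derived from one scale beside a power figure for a test on another.

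Weight is the only outcome that N.5 puts into real units. A reader will take N.5 to say that the average-difference test has 72% power for 2.5 kg. If patients' weights vary much more than 5 kg, that test would usually miss 2.5 kg, and a null result could be given more weight than it deserves.

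**Working it through.** **Inputs.** From N.5: f=.25, N=66, m=4 measures, r=.50, two-sided alpha 0.05, change SD 5 kg, difference 2.5 kg. Assumed: 1:1 allocation (33 per arm), equal correlation between visits, and a body-weight SD, S, which the documents do not give.

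**1. The plan's figures.** Between-group test: λ = f²Nm/[1+(m−1)r] = 0.0625×66×4/2.5 = 6.6. The noncentral F with 1 and 64 df gives 0.716, against the stated .7199. Trajectory test: λ = f²Nm/(1−r), with 3 and 192 df. This gives 0.999 at f=.25 (λ=33) and 0.828 at f=.15 (λ=11.88), against 0.99 and 0.83. The 5 kg enters none of these.

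**2. What the inputs imply for weight.** Under equal correlation, SD of change = S√[2(1−r)]. With 5 kg and r=.50, S = 5/√1 = 5 kg. At an assumed height of 1.75 m that is 5/1.75² = 1.6 BMI units.

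**3. What the documents suggest about S.** Of the men in Pilot Study 1 (IV.D.1), "37% were overweight and another 37% obese, with only 26% of normal weight". Take the cut-points as BMI 25 and 30 and assume normality. Then SD = 5/[z(.63)−z(.26)] = 5/(0.332+0.643) = 5.13, with mean 28.3. Restricted to BMI of 25 or more, the SD is 3.72. Multiplying by 1.75² gives 15.7 kg and 11.4 kg.

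**4. Main effect on raw weight.** Grant 2.5 kg at all four visits and hold the change SD at 5 kg, so r = 1−25/(2S²). The variance of a patient's mean is V = S²(1+3r)/4, and λ = 2.5²×66/(4V). For example, at S=10: r=0.875, V=90.6, λ=1.14, power 0.18.

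| Assumed S (kg) | implied r | power for 2.5 kg |
|---|---|---|
| 5 | 0.50 | 0.72 |
| 6 | 0.65 | 0.49 |
| 7.5 | 0.78 | 0.31 |
| 10 | 0.875 | 0.18 |
| 11.4 | 0.90 | 0.15 |
| 15 | 0.94 | 0.10 |
| 15.7 | 0.95 | 0.10 |
| 20 | 0.97 | 0.08 |

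Sensitivity:
- With r kept at .50, power is 0.24 at 10 kg and 0.10 at 20 kg.
- With no difference at baseline and 2.5 kg afterwards, the average difference is 1.875 kg, and power is 0.12 to 0.07 for S of 10 to 20 kg.
- With the preliminary difference of 11.8 lb (5.35 kg, section IV.E.2), power is 0.61 to 0.19 over the same range.

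**5. Contrasts that a change SD does fit.** For change from baseline averaged over weeks 8, 26 and 52, the correlation between changes is 0.5 whatever S is. The variance is 25×(1+2×0.5)/3 = 16.7, λ = 6.19, and power is 0.69. For mean post-baseline weight adjusted for baseline weight, the variance is S²[(1+2r)/3−r²]. This is 15.1 at S=10 (λ=6.83, power 0.73) and 16.3 at S=20 (λ=6.34, power 0.70).

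**The case against.** A reader might infer that .7199 is an arithmetic error and that the true power is 0.08 to 0.18. The documents do not support that. The figure follows from f, N, m and r, it reproduces, and as a standardised figure it can serve any continuous outcome in the plan. Only the sentence that turns f into kilograms uses the 5 kg.

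Three further objections have force.
- **The response variable is never named.** Raw weight is a strong inference from baseline being listed among the responses, but it is an inference. N.3 refers to an analysis-of-covariance design and allows covariates. If change is analysed, or baseline weight is adjusted for, power is about 0.69 to 0.73 and the gap nearly closes.
- **The body-weight SD is soft.** It rests on two BMI cut-points, a normal approximation and an assumed height. The pilot patients were acute inpatients not selected on this trial's criteria. Two women at 7% of the sample imply about 29 people (2/0.07), and the male percentages fit 27 men (7, 10 and 10).
- **The plan does not lead with this test.** N.5 names the trajectory difference as the main outcome.

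What remains is the mismatch itself. Eligibility has no upper BMI limit, so an SD of 5 kg is hard to credit, and power is already down to 0.49 at 6 kg. N.5 still offers .7199 for between-group comparisons, next to a 2.5 kg difference.

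**Conclusion.** The point holds for the kilogram translation, not for the F calculation. For a main effect on raw weight over four visits including baseline, .7199 and 2.5 kg are compatible only if body weight has an SD of about 5 kg. At an assumed SD of 10 to 20 kg, power for 2.5 kg is about 0.18 to 0.08; at the 11 to 16 kg suggested by the pilot it is about 0.15 to 0.10. These figures rest on raw weight being the response, equal correlation between visits, a change SD of 5 kg and an SD of weight that the documents do not state.

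A reader might also infer that the trial's main test is underpowered. This point gives no ground for that: between-patient variation in weight drops out of the group-by-time comparison, so the argument does not carry over to the 0.99 and 0.83.

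**What to change.** In N.5, state that 5 kg is an SD of weight change, and do not attach 2.5 kg to .7199 for a main effect on raw weight. For weight, quote between-group power for one of two contrasts: change from baseline averaged over weeks 8, 26 and 52 (about 0.69), or post-baseline weight adjusted for baseline weight (about 0.70 to 0.73 at an assumed SD of 20 to 10 kg). State the response variable, the SD and the correlation used.

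In N.4, add one sentence saying that any between-group comparison of average weight uses the chosen baseline-adjusted contrast, and leave the trajectory test as the main test.

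The cost is some rewording and, with the change-from-baseline contrast, a slightly less favourable figure (about 0.69 against .72). No extra patients or data are needed.
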